10.2. Definitions

10.2.1. Adverse Event (AE)

An AE is any untoward medical occurrence in a volunteer, which may occur during or after administration of an Investigational Medicinal Product (IMP) and does not necessarily have a causal relationship with the intervention. An AE can therefore be any unfavourable and unintended sign (including an abnormal laboratory finding), symptom or disease temporally associated with the study intervention, whether or not considered related to the study intervention.

10.2.2. Adverse Reaction (AR)

An AR is any untoward or unintended response to an IMP. This means that a causal relationship between the IMP and an AE is at least a reasonable possibility, i.e., the relationship cannot be ruled out. All cases judged by the reporting medical Investigator as having a reasonable suspected causal relationship to an IMP (i.e. possibly, probably or definitely related to an IMP) will qualify as adverse reactions.

10.2.3. Unexpected Adverse Reaction

An adverse reaction, the nature or severity of which is not consistent with the applicable product information in the Investigator Brochure (IB).

10.2.4. Serious Adverse Event (SAE)

An SAE is an AE that results in any of the following outcomes, whether or not considered related to the study intervention.

- Death
- Life-threatening event (i.e., the volunteer was, in the view of the Investigator, at immediate risk of death from the event that occurred). This does not include an AE that, if it occurred in a more severe form, might have caused death.
- Persistent or significant disability or incapacity (i.e., substantial disruption of one's ability to carry out normal life functions).
- Hospitalisation, regardless of length of stay, even if it is a precautionary measure for continued observation. Hospitalisation (including inpatient or outpatient hospitalisation for an elective procedure) for a pre-existing condition that has not worsened unexpectedly does not constitute a serious AE.
- An important medical event (that may not cause death, be life threatening, or require hospitalisation) that may, based upon appropriate medical judgment, jeopardise the volunteer and/or require medical or surgical intervention to prevent one of the outcomes listed above. Examples of such medical events include allergic reaction requiring intensive treatment in an emergency room or clinic, blood dyscrasias, or convulsions that do not result in inpatient hospitalisation.
- Congenital anomaly or birth defect.

10.2.5. Serious Adverse Reaction (SAR)

An adverse event (expected or unexpected) that is both serious and, in the opinion of the reporting Investigator or Sponsors, believed to be possibly, probably or definitely due to an IMP or any other study treatments, based on the information provided.

10.2.6. Suspected Unexpected Serious Adverse Reaction (SUSAR)

A serious adverse reaction, the nature and severity of which is not consistent with the information about the medicinal product in question set out in the IB.

NB: To avoid confusion or misunderstanding the following note of clarification is provided: "Severe" is often used to describe intensity of a specific event, which may be of relatively minor medical significance. "Seriousness" is the regulatory definition supplied above.

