10.3. Expected Serious Adverse Events

No serious adverse events are expected in this trial.

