10.5.1. Reporting Procedures for Serious AEs

In order to comply with current regulations on serious adverse event reporting to regulatory authorities, the event will be documented accurately and notification deadlines respected. SAEs will be reported on the SAE forms to members of the study team immediately the Investigators become aware of their occurrence, as described in the study's SOP. Copies of all reports will be forwarded for review to the Chief Investigator (as the Sponsor's representative) within 24 hours of the Investigator being aware of the suspected SAE. The data and safety monitoring board (DSMB) will be notified of SAEs that are deemed possibly, probably or definitely related to study interventions; the DSMB will be notified immediately (within 24 hours) of the Investigators' being aware of their occurrence. SAEs will be reported to the Research Ethics Committee (REC) at UVRI within 7 calendar days of the Investigator becoming aware of them, and a full report (if the initial report is not complete) will be made within 7 calendar days of the initial report. SAEs will not normally be reported immediately to the Oxford or LSHTM ethical committee(s) unless there is a clinically important increase in occurrence rate, an unexpected outcome, or a new event that is likely to affect safety of trial volunteers, at the discretion of the Chief Investigator and/or DSMB. In addition to the expedited reporting above, the Investigator shall include all SAEs in the annual Development Safety Update Report (DSUR) report.

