10.5.2. Reporting Procedures for SARs

These will be reported as per any SAE.

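### Section 10.2.6 needs nature and severity to depart from the IB for a SUSAR, where 10.2.3 needs only one; read literally, some unexpected serious reactions can miss the mandatory 7/15-day reports

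*Combined protocol and SAP*

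**What the plan says.** Three places in the protocol bear on whether a serious reaction is unexpected.

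- Section 10.2.3 gives the test for unexpectedness as follows: "An adverse reaction, the nature or severity of which is not consistent with the applicable product information in the Investigator Brochure (IB").
- Section 10.2.6 defines a SUSAR as "A serious adverse reaction, the nature and severity of which is not consistent with the information about the medicinal product in question set out in" that brochure. It does not refer back to 10.2.3.
- Section 10.3: "No serious adverse events are expected in this trial".

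The classification decides the reporting route. For a serious adverse reaction (SAR) that is not a SUSAR, section 10.5.2 says only: "These will be reported as per any SAE". Under 10.5.1, the Chief Investigator receives a copy within 24 hours. For related events, "the DSMB will be notified immediately (within 24 hours) of the Investigators' being aware of their occurrence". For the local committee, "SAEs will be reported to the Research Ethics Committee (REC) at UVRI within 7 calendar days of the Investigator becoming aware of them". The other two committees are treated differently: "SAEs will not normally be reported immediately to the Oxford or LSHTM ethical committee(s"), with exceptions at the discretion of the Chief Investigator and/or the DSMB. One of those exceptions is an unexpected outcome.

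For a SUSAR, section 10.5.3 keeps the 7-day report to the UVRI REC. It adds mandatory reports by the Chief Investigator to the MHRA and to the Oxford and LSHTM committees, within 15 days or within 7 if life threatening. It also requires Investigators to be told of relevant safety information.

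**The concern.** The same test is joined by *or* in one definition and by *and* in the other. A serious related reaction of a kind already described in the IB, but worse than described, is unexpected under 10.2.3. Read literally, it is not a SUSAR under 10.2.6. The same holds for a reaction of a new kind whose severity is not out of line with the IB.

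The first case is realistic here. Section 5.4.1 records transient lymphopenia and neutropenia after ChAdOx1 85A, and 10.2.4 gives blood dyscrasias as an example of a serious event. A serious cytopenia would then be a known type at greater severity. This assumes that the IB, which is not among the documents, describes the same findings.

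At stake is whether the fixed-clock reports in 10.5.3 are made. Within section 10.5, that is the only route for an individual event that combines a named regulator with a fixed deadline. Before this trial the ChAdOx1 85A prime had been given to 42 UK adults (section 5.4.1), and here it goes to adolescents.

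**Working it through.** No sample size, power or event rate enters, so the check is a comparison of definitions and then of routes.

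**Step 1. Definitions.** Take a serious, related reaction and ask whether its nature and its severity depart from the IB.

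| Nature departs | Severity departs | Unexpected (10.2.3, *or*) | SUSAR (10.2.6, literal *and*) | Agree? |
|---|---|---|---|---|
| yes | yes | yes | yes | yes |
| yes | no | yes | no | no |
| no | yes | yes | no | no |
| no | no | no | no | yes |

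Section 10.2.3 captures 3 of the 4 combinations and literal 10.2.6 captures 1, so they disagree in 3 − 1 = 2. These are counts of combinations, not probabilities.

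If 10.3 is taken as a classification rule, all 4 combinations are unexpected and the gap closes. Section 10.2.6 does not cite 10.3, so the documents do not say which standard governs.

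**Step 2. Routes for the two disputed combinations.**

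| Report or action | If handled as SAR | If handled as SUSAR |
|---|---|---|
| Holding rule (10.1, 10.1.1) | applies | applies |
| Chief Investigator, 24 hours (10.5.1) | applies | applies |
| DSMB, 24 hours (10.5.1, 10.8) | applies | applies |
| UVRI REC, 7 calendar days (10.5.1, 10.5.3) | applies | applies |
| Oxford and LSHTM committees | discretionary (10.5.1) | mandatory, 7/15 days (10.5.3) |
| MHRA | no individual report named | mandatory, 7/15 days (10.5.3) |
| Notice to Investigators | not stated | required where relevant to safety (10.5.3) |

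Only the last three rows depend on the classification.

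**Step 3. After the change.** With *or* in 10.2.6, a SUSAR covers 3 of 4 combinations and the disagreement with 10.2.3 falls from 2 to 0. The fourth combination, where neither element departs, then depends only on how 10.3 is meant.

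**The case against.** The strongest reply is that 10.3 already answers the question: if no serious event is expected, every SAR is unexpected and goes through 10.5.3. That is a fair reading, but not a secure one. Section 10.3 states an expectation, not a reporting rule. Section 10.2.5 defines SARs so as to include both expected and unexpected events, and 10.5.2 gives SARs a route of their own. That route would have no use if every SAR were a SUSAR.

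A second reply is grammatical. The singular verb in 10.2.6 allows nature and severity to be read as one joint description that fails if either part departs, which would match 10.2.3. This is possible, and nothing in the documents shows that staff would apply the strict reading. But a reporting trigger should not turn on that choice when a neighbouring definition uses *or* for the same test.

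A third reply is that other safeguards remain, and this stands in full. Any SAE judged possibly, probably or definitely related activates the holding rule in 10.1.1, whether or not it is a SUSAR. The randomised trial is then held and the DSMB consulted (10.1), and the local ethics committee and manufacturers are told. The 24-hour and 7-day reports are unchanged. The discretionary exceptions in 10.5.1 could well bring the event to Oxford and LSHTM. Section 15.3 also does not list the MHRA among this trial's authorities, and 10.5.1 and 10.5.3 do not name the Ugandan regulator, so the wording in 10.2.6 does not alter any stated route to that regulator.

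A reader might therefore infer that the *and* removes expedited review of a reaction worse than the IB describes, or that such a reaction is bound to miss the SUSAR route. The documents support neither. Rapid local and DSMB review continues, and the miss follows only on the literal reading with 10.3 set aside.

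**Conclusion.** The inconsistency between 10.2.3 and 10.2.6 is real and is in the current text. On the literal reading, 2 of 4 nature-by-severity combinations can lose the mandatory 7/15-day reports to the MHRA and the Oxford and LSHTM committees, together with the notice to Investigators. This rests on two assumptions: that *and* is read strictly, and that 10.3 is not applied as a rule making every SAR unexpected.

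Few events should be affected. Section 5.4.1 reports one possible SAR in over 2500 MVA85A recipients and no SAEs in 42 ChAdOx1 85A recipients. The effect is on how each such event is handled, not on any estimate, sample size or analysis. It is worth correcting because it is safety reporting and the correction is small.

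**What to change.** In 10.2.6, replace *and* with *or* between nature and severity, so that a SUSAR is a serious adverse reaction that is unexpected as defined in 10.2.3. Add one sentence reconciling this with 10.3: state whether, because no serious events are expected, any SAR is to be treated as unexpected for reporting. If the answer is yes, 10.5.2 should say so, since its separate route for SARs would then no longer be used.

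The cost is one word, one clarifying sentence (plus a line in 10.5.2 if needed) and at most a few more expedited reports.

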10.3. Expected Serious Adverse Events

No serious adverse events are expected in this trial.

10.4. Causality Assessment

For every AE, an assessment of the relationship of the event to the administration of the vaccine will be undertaken by the CI-delegated clinician. An intervention-related AE refers to an AE for which there is a probable or definite relationship to administration of a vaccine. An interpretation of the causal relationship of the intervention to the AE in question will be made, based on the type of event; the relationship of the event to the time of vaccine administration; and the known biology of the vaccine therapy (Table 7). Alternative causes of the AE, such as the natural history of pre-existing medical conditions, concomitant therapy, other risk factors and the temporal relationship of the event to

vaccination will be considered and investigated. Causality assessment will take place during planned safety reviews, interim analyses (e.g. if a holding or stopping rule is activated) and at the final safety analysis, except for SAEs, which should be assigned by the reporting investigator.

0	No Relationship	No temporal relationship to study product and Alternate aetiology (clinical state, environmental or other interventions); and Does not follow known pattern of response to study product
1	Unlikely	Unlikely temporal relationship to study product and Alternate aetiology likely (clinical state, environmental or other interventions) and Does not follow known typical or plausible pattern of response to study product.
2	Possible	Reasonable temporal relationship to study product; or Event not readily produced by clinical state, environmental or other interventions; or Similar pattern of response to that seen with other vaccines
3	Probable	Reasonable temporal relationship to study product; and Event not readily produced by clinical state, environment, or other interventions or Known pattern of response seen with other vaccines
4	Definite	Reasonable temporal relationship to study product; and Event not readily produced by clinical state, environment, or other interventions; and Known pattern of response seen with other vaccines

Table 7. Guidelines for assessing the relationship of vaccine administration to an AE

10.5. Reporting Procedures for All Adverse Events

All local and systemic AEs occurring in the 28 days following each vaccination observed by the Investigator or reported by the volunteer, whether or not attributed to study medication, will be recorded. Recording and reporting of all AEs will take place as detailed in the study's SOP. All AEs that result in a volunteer's withdrawal from the study will be followed up until a satisfactory resolution occurs, or until a non-study related causality is assigned (if the volunteer consents to this). Serious adverse events (SAEs) will be collected throughout the entire trial period.

Adverse event	
Local	Pain/tenderness at the injection site
	Swelling at injection site
	Warmth at the injection site
	Itch at the injection site
	Scaling/pustules at the injection site
Systemic	Documented fever (temperature > 37.5° C)
	Myalgia
	Arthralgia
	Feverishness
	Headache
	Fatigue
	Nausea
	Malaise

Table 8. Routinely solicited adverse events

10.5.1. Reporting Procedures for Serious AEs

In order to comply with current regulations on serious adverse event reporting to regulatory authorities, the event will be documented accurately and notification deadlines respected. SAEs will be reported on the SAE forms to members of the study team immediately the Investigators become aware of their occurrence, as described in the study's SOP. Copies of all reports will be forwarded for review to the Chief Investigator (as the Sponsor's representative) within 24 hours of the Investigator being aware of the suspected SAE. The data and safety monitoring board (DSMB) will be notified of SAEs that are deemed possibly, probably or definitely related to study interventions; the DSMB will be notified immediately (within 24 hours) of the Investigators' being aware of their occurrence. SAEs will be reported to the Research Ethics Committee (REC) at UVRI within 7 calendar days of the Investigator becoming aware of them, and a full report (if the initial report is not complete) will be made within 7 calendar days of the initial report. SAEs will not normally be reported immediately to the Oxford or LSHTM ethical committee(s) unless there is a clinically important increase in occurrence rate, an unexpected outcome, or a new event that is likely to affect safety of trial volunteers, at the discretion of the Chief Investigator and/or DSMB. In addition to the expedited reporting above, the Investigator shall include all SAEs in the annual Development Safety Update Report (DSUR) report.

10.5.2. Reporting Procedures for SARs

These will be reported as per any SAE.

10.5.3. Reporting Procedures for SUSARs

The Principal Investigator will report all SUSARs to the UVRI REC within 7 calendar days of the Investigator becoming aware of them, and a full report (if the initial report is not complete) will be made within 7 calendar days of the initial report. The Chief Investigator will report all SUSARs to the MHRA and Oxford and LSHTM ethical committee(s) within required timelines (15 days for all SUSARs, unless life threatening in which case 7 days, with a final report within a further 8 days (total 15)). The Chief Investigator will also inform all Investigators concerned of relevant information about SUSARs that could adversely affect the safety of volunteers. All SUSARs and deaths occurring during the study will be reported to the Sponsor. For all deaths, available autopsy reports and relevant medical reports will be made available for reporting to the relevant authorities.

10.5.4. Development Safety Update Report

A Development Safety Update Report (DSUR) will be submitted by the Sponsor to the UK competent authority and ethical committee on the anniversary of the first approval date from the regulatory authority for each IMP, in accordance with UK regulatory requirements.

10.6. Assessment of Severity

The severity of clinical and clinical laboratory adverse events will be assessed according to the scales in Table 9-11. Clinical laboratory adverse events will be assessed as grade 1 if 1.1 to 2.4 times the limit of normal, grade 2 if 2.5 to 4.9 times, and 3 if greater than 5 times the limit of normal, in accordance with FDA guidance for toxicity grading. Normal ranges will be based on those defined locally by Lugada and colleagues for haematology [61], and those provided by the ISO accredited Clinical Diagnostic Laboratory at UVRI for biochemistry.

Adverse Event	Grade	Intensity
Pain at injection site	1	Pain that is easily tolerated
	2	Pain that interferes with daily activity
	3	Pain that prevents daily activity
Erythema at injection site*	1	>3 - ≤50 mm
	2	>50 - ≤100 mm

	3	>100 mm
Swelling at injection site	1	>1 - ≤20 mm
	2	>20 - ≤50 mm
	3	>50 mm

Table 9. Severity grading criteria for local adverse events

*erythema ≤3mm is an expected consequence of skin puncture and will therefore not be considered an adverse event

	Grade 1 (mild)	Grade 2 (moderate)	Grade 3 (severe)
Fever	37.6°C - 38.0°C	38.1°C – 39.0°C	>39.0°C
Tachycardia (bpm)*	101 - 115	116 – 130	>130
Bradycardia (bpm)**	50 – 54	40 – 49	<40
Systolic hypertension (mmHg)	141 - 159	160 – 179	≥180
Diastolic hypertension (mmHg)	91 - 99	100 – 109	≥110
Systolic hypotension (mmHg)***	85 - 89	80 – 84	<80

Table 10. Severity grading criteria for physical observations [appropriate adjustments will be made for age, gender and height percentiles]

*Taken after ≥10 minutes at rest; **When resting heart rate is between 60 – 100 beats per minute. Use clinical judgement when characterising bradycardia among some healthy volunteer populations, for example, conditioned athletes; ***Only if symptomatic (e.g. dizzy/ light-headed)

GRADE 0	None
GRADE 1	Mild: Transient or mild discomfort (< 48 hours); no medical intervention/therapy required
GRADE 2	Moderate: Mild to moderate limitation in activity – some assistance may be needed; no or minimal medical intervention/therapy required
GRADE 3	Severe: Marked limitation in activity, some assistance usually required; medical intervention/therapy required, hospitalisation possible

Table 11. Severity grading criteria for respiratory and systemic AEs

10.7. Procedures to be followed in the event of abnormal findings

Eligibility for enrolment in the trial in terms of laboratory findings will be assessed as detailed in Section 7. Abnormal clinical findings from medical history, examination or blood tests will be assessed as to their clinical significance throughout the trial. Laboratory adverse events will be assessed using the normal ranges based on those defined locally by Lugada and colleagues for haematology [61], and those provided by the ISO accredited Clinical Diagnostic Laboratory at UVRI for biochemistry. If a test is deemed clinically significant, it may be repeated, to ensure it is not a single occurrence. If a test remains clinically significant, the volunteer will be informed and appropriate medical care arranged as appropriate and with the permission of the volunteer. Specific details regarding findings, discussion with volunteers and resulting actions will be recorded in the CRF. Decisions to exclude the volunteer from enrolling in the trial or to withdraw a volunteer from the trial will be at the discretion of the Investigator.

10.8. Data and Safety Monitoring Board (DSMB)

A data and safety monitoring board (DSMB) will be appointed to provide real-time safety oversight. The DSMB will be notified within 24 hours of the Investigators' being aware of the occurrence of SAEs. The DSMB has the power to place the trial on hold if deemed necessary following a trial intervention-related SAE. The DSMB will be chaired by clinician experienced in early-phase clinical trials. There will be a minimum of two other appropriately qualified committee members. Membership will include a statistician, and at least one Ugandan member. All correspondence between Investigator and DSMB will be conveyed by the Chief Investigator to the trial Sponsor. The Chair of the DSMB will be contacted for advice and independent review by the Investigator or trial Sponsor in the following situations:

- Following any SAE deemed to be possibly, probably, or definitely related to the trial challenge agent.
- Any other situation where the Investigator or trial Sponsor feels independent advice or review is important.

Reports will be provided to the DSMB on completion of recruitment to groups 1 and 2 (adult dose escalation) before proceeding to group 3; and on completion of recruitment to groups 3 and 4 (adolescent dose escalation), before proceeding to the randomised trial (groups 5 and 6).

11. STATISTICS

This is primarily an exploratory immunogenicity and safety trial with descriptive endpoints.

Adverse events will be listed and summarised by type of AE, frequency, severity and trial group.

The sample size (12 participants for dose escalation and age de-escalation, 60 participants [30 in each arm] for the randomised trial) has been determined by the number of doses of ChAdOx1 85A available for this study. The following are the considerations regarding sample size for the randomised component of the trial. The primary outcome is the IFN- γ ELIspot response to antigen 85A at week 9 which is measured in spot forming counts per 1×10^6 peripheral blood mononuclear cells (PBMCs). Assuming a standard deviation of $0.4 \log_{10}$ sfc/ 1×10^6 PBMC (spot forming counts/ 1×10^6 peripheral blood mononuclear cells) in the peak Ag85A response, our study will have over 80% power to detect a difference of $0.29 \log_{10}$ in sfc/ 10^6 PBMC with $p < 0.05$. This is comparable to the difference that was observed between the response to human adenovirus vectored TB vaccine candidate Aeras 402 alone (Day 14 post Aeras) and Aeras 402 with MVA85A boost (Day 7 post MVA boost) [21], or between BCG (Day 28) and MVA85A alone (Day 7) in UK subjects [62], and hence a reasonable difference to expect between BCG and ChAdOx1 85A-MVA85A (aim 2).

For outcomes that are approximately normally distributed or normalised by log-transformation, differences in means will be presented together with 95% confidence intervals and p-values from unpaired t-tests. For non-normally distributed outcomes, the difference in medians between the two groups will be presented along with its 95% confidence intervals, and p-values from Wilcoxon ranksum tests.

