- b. Number of subjects is actual number enrolled for studies that have completed enrolment, and planned number of subjects for studies in which enrolment is ongoing or which are still blinded
- c. EPI deferred for 1 week
- d. Enrolment in TB017 was terminated early, due to issues with the supply of the FP85A vaccine
- e. Subjects blinded as to whether they received MVA85A via the ID or aerosol inhaled route
- f. 47 subjects were randomised to receive MVA85A with EPI and 48 were randomised to receive MVA85A alone. As a result of an error, 1 subject switched groups, resulting in 48 subjects receiving MVA85A with EIP and 47 receiving MVA85A alone
- g. Two of the 1398 subjects randomised to the Candin® group were not vaccinated
- h. Two of these 16 subjects were vaccinated with AERAS-402 but discontinued from the study before receiving MVA85A
- i. One of the 324 subjects randomised to MVA85A/AERAS-485 was not vaccinated; one subject randomised to Candin® received MVA85A/AERAS-485
- j. The subjects, the bronchoscopist and immunologists were blinded to treatment assignment; the investigator administering the vaccinations was not blinded
- k. One subject withdrew post first vaccination but prior to boost vaccination, and was replaced
- l. Starter group not blinded. For groups A and B the subjects, the bronchoscopist, and immunologists are blinded to treatment assignment; the investigator administering the vaccinations is not blinded.

Safety profile

No signs of any Koch reaction (i.e. exacerbation of tissue damage at a focus of TB infection) have been seen in volunteers infected with *M.tb* with this or any other candidate TB vaccine to date. One possible vaccine related SAE – early unmasking of pre-existing tuberculous meningitis - occurred in a patient with HIV in South Africa.

Typical local and systemic reactions to IM injection, and the preliminary analysis of local and systemic reactions induced by the aerosol route that were reported in the completed Phase I safety trial are summarised in section 5.3 “Risks and Benefits”.

Dosing

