7.12. Discontinuation / Withdrawal Criteria

In accordance with the principles of the current revision of the Declaration of Helsinki and any other applicable regulations, a volunteer has the right to withdraw from the study at any time and for any reason, and is not obliged to give his or her reasons for doing so. The Investigator may withdraw the volunteer at any time in the interests of the volunteer's health and well-being. In addition the volunteer may withdraw/be withdrawn for any of the following reasons:

- Administrative decision by the Investigator.
- Ineligibility (either arising during the study or retrospectively, having been overlooked at screening).
- Significant protocol deviation.
- Volunteer non-compliance with study requirements.
- An AE, which requires discontinuation of the study involvement or results in inability to continue to comply with study procedures.

Any volunteer who becomes pregnant during the trial will be followed up as per the protocol and until the end of the pregnancy. The babies will also be followed up and examined for any adverse effects. We will not routinely perform venepuncture in a pregnant volunteer.

The reason for withdrawal will be recorded in the CRF. If withdrawal is due to an AE, appropriate follow-up visits or medical care will be arranged, with the agreement of the volunteer, until the AE has

resolved, stabilised or a non-trial related causality has been assigned. Any volunteer who is withdrawn from the study may be replaced, if that is possible within the specified time frame. Any volunteer who fails to attend for two or more follow-up visits during the study will be deemed to have withdrawn from the study.

If a volunteer withdraws from the study, blood samples collected before their withdrawal from the trial will be used/ stored unless the volunteer specifically requests otherwise.

In all cases of subject withdrawal, excepting those of complete consent withdrawal, long-term safety data collection, including some procedures such as safety bloods, will continue as appropriate if subjects have received one or more vaccine doses.

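### The stated power of over 80% needs a normal approximation and all 60 participants evaluable; the planned t-test gives about 79%, with no allowance for loss

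*Combined protocol and SAP*

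**What the plan says.** Section 11 (Statistics) gives the size as "60 participants [30 in each arm] for the randomised trial" and says that it was set by the ChAdOx1 85A doses available. It then offers a power statement for the primary outcome, the ELISpot response to antigen 85A at week 9. With an SD of 0.4 log10 and a significance level of 0.05, "our study will have over 80% power to detect a difference of" 0.29 log10. Neither the formula nor the sidedness is given, and no allowance is made for missing results.

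For normal or log-normal outcomes, the same section says that "differences in means will be presented together with 95% confidence intervals" and "p-values from unpaired t-tests". A rank-sum test is kept for outcomes that are not normal.

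Three other places bear on how many participants will be evaluable:

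- **Sections 7.9 and 8.4.2.** Group 5 returns for an MVA85A boost before the endpoint. This is at day 56 for new enrolees and up to 52 weeks after the prime for those enrolled before the lockdown.
- **Section 7.12.** "Any volunteer who is withdrawn from the study may be replaced, if that is possible within the specified time frame".
- **Table 2, footnote h**, on one arm of TB032, an AERAS-402/MVA85A trial: "Two of these 16 subjects were vaccinated with AERAS-402 but discontinued from the study before receiving MVA85A".

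**The concern.** The power claim is a threshold claim: over 80%. It should hold for the analysis that will be run and for the number of participants likely to supply the endpoint. It appears to do neither.

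The t-test has to estimate the SD, so it has slightly less power than a normal approximation, and here the approximation clears 80% by only 0.2 points. The calculation also treats all 30 per arm as evaluable, although the group 5 endpoint depends on a return visit for a second vaccine. A group 5 participant who has already been primed can be replaced only by using another ChAdOx1 85A dose, and dose supply is what capped the trial.

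What is at stake is how the comparison with BCG revaccination is read. If no difference is found, the protocol's figure would credit the trial with slightly more power than its own analysis provides.

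**Working it through.** **Inputs, from Section 11 unless noted**

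- n = 30 per arm; SD = 0.4 log10; difference = 0.29 log10.
- Significance level 0.05. Two-sided is inferred from the 95% confidence intervals, because the plan does not state it.
- Test: unpaired t-test.
- Loss: none stated. The range below is an assumption. Its ends are 2 and 4 of 30, which correspond to TB032's 2 of 28 over both MVA85A-boosted arms (7.1% × 30 = 2.1) and 2 of 16 in one arm (12.5% × 30 = 3.75).

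**Step 1: reproduce the stated figure (normal approximation, 30/30)**

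SE = 0.4 × √(1/30 + 1/30) = 0.1033

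δ = 0.29 / 0.1033 = 2.808

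Power = Φ(2.808 − 1.960) = Φ(0.848) = 80.2%

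The inverse formula agrees: n = 2 × (1.960 + 0.842)² × 0.4² / 0.29² = 29.9, rounded up to 30 per arm. This method fits the stated figure.

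**Step 2: the planned t-test (30/30)**

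Power = P(|T| > t crit), where T is noncentral t with n1 + n2 − 2 degrees of freedom and noncentrality δ.

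With 58 degrees of freedom, t crit = 2.002 and δ = 2.808, so power = 78.8%. The shortfall against Step 1 is about 1.3 points. Reaching 80% takes 31 evaluable per arm (80.2%), or a difference of 0.294 log10 with 30 per arm.

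**Step 3: loss without replacement**

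δ = 0.29 / [0.4 × √(1/n1 + 1/n2)]

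| Evaluable (group 5 / group 6) | δ | t-test | Normal approximation | Difference with 80% power (t-test) |
|---|---|---|---|---|
| 30 / 30 | 2.808 | 78.8% | 80.2% | 0.294 |
| 29 / 30 | 2.784 | 78.1% | 79.5% | 0.297 |
| 28 / 30 | 2.759 | 77.4% | 78.8% | 0.300 |
| 26 / 30 | 2.706 | 75.7% | 77.2% | 0.306 |
| 28 / 28 | 2.713 | 75.9% | 77.4% | 0.305 |
| 26 / 26 | 2.614 | 72.7% | 74.4% | 0.317 |

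No row reaches 80% by the two-sided t-test. By the normal approximation, only the row with complete data does.

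**Step 4: sensitivity to sidedness**

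A one-sided 5% t-test at 30/30 would give 87.1%. Nothing in Section 11 states a one-sided test, and the 95% intervals point to a two-sided one.

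**The case against.** The strongest reply is that nothing is miscalculated. The figure follows from a standard formula, the gap to the t-test is 1.3 points, and 0.294 rounds to the protocol's 0.29. The SD is given to one significant figure: an SD of 0.39 gives 80.8% by t-test, and SDs from 0.35 to 0.45 give 88% down to 69%. The trial is described as exploratory with descriptive endpoints, and a null result would be read mainly from its confidence interval. All of this stands, and it is why the point is minor. It does not make the sentence true for the planned test on the stated inputs.

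A reader might infer three stronger points. The documents support none of them.

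- **That the real power is 73% to 76% because 12.5% will be lost before the boost.** That rate is 2 of 16 in one arm of UK adults given a different vector. Both boosted TB032 arms together give 2 of 28. The closest precedent, TB034 (Section 5.1.5), used the same two vaccines and reports no loss in its boosted groups of 12. Its Wilcoxon p-value of 0.0005 after the boost equals the smallest two-sided exact value for 12 pairs (2/2¹² = 0.0005), which suggests that all 12 were evaluable. Section 7.12 also allows replacement, and full replacement returns power to 78.8%. Recruitment from an established cohort, selection partly on good attendance, and the option of school visits all favour retention.
- **That 73% is the effect of boost loss.** Group 6 has no boost. Four losses in group 5 alone give 75.7%. The 72.7% figure also needs four losses in the BCG arm, for which the documents give no source.
- **That the power statement is the only justification for the sample size.** Section 11 says that dose supply determined it.

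In addition, the boost delay of up to 52 weeks applies only to those enrolled before the lockdown, and a missed boost does not by itself mean a missing ELISpot. These facts limit how much loss to expect. They do not supply the missing allowance.

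**Conclusion.** The concern holds as a minor point. On the plan's own SD, difference and sample size, over 80% is reached only by a two-sided normal approximation with all 60 participants evaluable (80.2%). The planned unpaired t-test gives 78.8% with complete data. This rests on the test being two-sided, which is inferred.

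The plan makes no allowance for loss. If 2 to 4 of 30 were lost without replacement in group 5 only, power would be about 77% to 76%. The same loss in both arms would give about 76% to 73%. These are illustrations under an assumption, not forecasts, and the documents do not establish an expected rate.

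The effect on interpretation is modest, because the size was set by supply and the trial is exploratory.

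**What to change.** In Section 11, replace the power sentence with wording such as:

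> With 30 evaluable participants per arm and an SD of 0.4 log10, a two-sided 5% unpaired t-test has about 79% power for a difference of 0.29 log10 (80% for 0.294 log10). Assuming for illustration that 2 to 4 of 30 are lost without replacement, power is about 77% to 76% if the loss is in group 5 only, and about 76% to 73% if it is the same in both arms.

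This also states the sidedness and the test. Keep the loss range labelled as an assumption, do not enter 12.5% as a planning rate, and leave the sample size unchanged. The cost is two sentences and a slightly less favourable stated power. No design feature changes.
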